4.2 Familiarisation Session

This can be conducted on the same day as the signing of the informed consent forms. The patient should be given the opportunity to experience the feeling of TMS prior to commencing with the experimental sessions. The participant will have a fabric cap placed on their head, with a grid drawn on it, indicating the midpoint (vertex) of the head and locations relative to it. The TMS coil will be positioned on the head over the motor cortex on the healthy hemisphere (5cm lateral and 1cm anterior from the vertex), and a weak magnetic pulse applied. The patient will be asked whether they can feel anything. The intensity of the pulses will then be turned up gradually, asking the participant with each increment if the pulse still feels comfortable. When the stimulation intensity is sufficient to evoke a response (MEP) in the index finger muscle of at least 50uV, 5 such pulses will be applied with intervals between 6-8 seconds, to establish the average MEP amplitude at this scalp location. The coil position will then be moved left and right, forwards, and backwards at 1cm increments relative to the starting position, until the position with the largest and most reliable MEPs is located (the motor 'hotspot'). On the hotspot, the experimenter will next establish the patients *resting motor threshold* (RMT). That is, the lowest stimulation intensity that produces MEPs greater than 50uV on 5/10 trials.

When the hotspot and RMT have been established on the healthy hemisphere, this procedure will be repeated on the stroke affected hemisphere, guided by the knowledge of motor cortex positioning on the healthy hemisphere. The RMT is typically much higher on the stroke affected hemisphere, so a higher intensity of stimulation will be required to evoke responses. The RMT for both hemispheres will be noted for future reference, and the position of the hotspot on both hemispheres will be noted on the fabric cap. This is to assist positioning of the TMS coil for all subsequent sessions and negate the need for extensive mapping of the scalp on each new day of testing.

The patient will then be familiarised with the mental imagery requirements of the protocol. They will then be asked to imagine the *feeling* of performing movements with the stroke affected limb and told that this type of imagery will be required to influence the amplitude of their MEPs during the training sessions.

At this stage, if the patient has no MEPs in response to TMS, unfortunately they will not be able to participate further in the study (or, if willing, try again in a week to see have MEPs recovered).

4.3 Baseline Functional and Cognitive Assessments

Prior to commencing the first TMS NF training session, the patient will have their upper limb function assessed by a member of the team (not the same member who will perform the TMS, for blinding reasons). They will perform the Fugl-Meyer task assessing the quality of a range of upper limb movements, and the Action Research Test (keeping a long break between these two tests to avoid fatigue or coming back on a separate day to perform one of the two functional tests). They will complete standard questionnaires assessing cognitive function and mood/depression (the Oxford Cognitive Screen, and the Hospital Affective Disorders Scale). They will also complete the National Institute of Health Stroke severity scale (NIHSS), Motor imagery ability questionnaire, a sleep questionnaire and measure muscle circumference in forearm and bicep of both arms.

If all tests above conducted together, estimated time is approx. 1 hour 30 minutes, so allow 2 hours for this session with comfort break for patient.

4.4 MRI scanning

Following the familiarisation session and baseline functional and cognitive assessments, the patients will be invited to undergo a series of MRI brain scans in the Centre for Advanced Medical Imaging (CAMI), on the site of St. James Hospital. Total scanning time will be 1 hour per participant, which will comprise of the following types of scans:

1. High resolution T1 anatomical scan (grey matter)
2. Diffusion weighted imaging (DWI) scan (white matter)

4.5 TMS NF training sessions 1-4

4.5.1 Training sessions overview

The TMS sessions should be spaced at maximum of 72 hours apart, ideally session 1-4 should occur all within the same 7-day period.

When the patient arrives for each training session, they will sit in a comfortable chair or bed with arms supported on foam pillows and have their muscles prepared with exfoliant skin preparation paste and an alcohol wipe. Electrodes will be placed over the target muscles (hand and arm muscles).

The research team will place the TMS coil over the hotspot that was located during the familiarisation session. On this location (separately for healthy and stroke affected hemisphere), we will measure the patients RMT.

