In the absence of being able to generate movement in the paretic limb, motor imagery has been suggested to activate many of the same brain-muscle circuits as actual movement. However, as imagery is a hidden mental process, it is impossible for individuals to gauge what impact this is having upon their neural activity, to learn how to best exploit this mechanism to augment stroke recovery.

This research project is an investigation into the mechanisms and efficacy of using a novel brain-computer interface (BCI) (eg. Ruddy et al., 2018) based upon muscle responses to TMS to provide feedback (visual and auditory) to stroke survivors while they perform motor imagery.

Using this approach, magnetic pulses will be applied to the scalp over the location on the motor cortex that controls the arm and hand, via TMS. This evokes a twitch in the stroke-affected muscles (the MEP), which is recorded using electromyography (EMG). The size of MEPs are displayed to the patient in real-time, with rewarding visual and auditory feedback incorporated in a game-like display. The patient is instructed to learn how to make MEPs bigger using motor imagery, guided by the feedback from the brain-computer interface.

We hypothesise that training using TMS-neurofeedback will lead to increases in MEP amplitudes, compared to a control group receiving pseudofeedback. We will investigate whether these changes in MEP amplitudes correlate with enhanced or faster than usual functional improvement and explore the underlying structural and neurochemical brain mechanisms of recovery.

2. Patient characteristics and exclusion criteria

20 patients (10 in TMS NF group, 10 in Pseudo-feedback group). Sub-acute: 2-26 weeks post stroke. Would prefer 2-12 weeks if feasible as there is a critical period in first 12 wks. First stroke (no previous TIAs). Single Hemisphere lesion. Low/No residual movement in lower arm and hand. MEP positive (in response to TMS). No or negligible OCS broken hearts cancellation test score (visual neglect) 6. No or almost no cognitive impairment (Pass or near pass MMSE and MOCA) 7. Passes TMS-Safety Questionnaire (no contraindications to TMS)

3. Recruitment Procedure

Patients informed about the study directly via consultant [name] and his team and provided with information sheets detailing how to contact the researchers if interested.

4. Procedures with Patients

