4.1 Informed Consent and Providing Information

The patient should be asked to read through the information sheet prior to coming to the first day of the experiment. However, when they arrive for the first session, provide them again with the information sheets and go through them page by page reading and explaining everything to them, answering any questions. When the patient has understood everything, read through the consent form with them, answering any questions, and if they consent to participate ask them to sign their name. If they are unable to sign the consent form, their next of kin can provide consent by proxy. At this stage they will be assigned an

anonymous code which will be used to identify their data and assigned to Group A or Group B using a computer algorithm.

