4.5.2 TMS neurofeedback block

The patient will be positioned in front of a computer monitor and will receive a block of 20 neurofeedback trials. Each trial contains just one TMS pulse, so in total they will receive 20 TMS pulses (at an intensity that is 120% of the RMT) with an interval of 6-8 seconds between pulses. Each TMS pulse will be followed immediately by feedback on screen in the form of a vertical bar. The height of the bar indicates the amplitude of the MEP recorded in the muscle, and this is shown relative to a horizontal white line that indicates their baseline MEP amplitude. If the current MEP on a given trial is larger than baseline, the trial is deemed 'successful'. The vertical bar will be green, with a green tick on screen beside it, and a positive sound-byte will be played. If the MEP amplitude is below baseline, the trial is unsuccessful; The bar will be red, with a red cross, and a negative sound-byte will be played. Patients will be told that their goal is to accrue as many successful trials as possible, and that the height of the bar can be influenced by imagining movements using the stroke affected limb (specifically, the stroke affected finger muscles).

This block of neurofeedback takes approximately 6 minutes, and is repeated three times during the course of the training session, with rest breaks for the patient between blocks.

At the end of the training session, we will record MEPs from 20 TMS pulses while the patient is at rest, viewing a fixation cross (for pre-post measurement of resting corticospinal excitability).

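### Blinding covers only the upper-limb assessor; nothing in the visible protocol keeps the feedback display from whoever applies TMS, although the stated hypothesis concerns MEP amplitude

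*Protocol*

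**What the plan says.** Section 1 states one hypothesis: "We hypothesise that training using TMS-neurofeedback will lead to increases in MEP amplitudes, compared to a control group receiving pseudofeedback". Functional improvement comes in as something to be correlated with the MEP changes. Section 2 plans "20 patients (10 in TMS NF group, 10 in Pseudo-feedback group").

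Blinding is mentioned once, in section 4.3. Upper-limb function is assessed by a team member who is "not the same member who will perform the TMS, for blinding reasons".

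The stimulation side is described as follows.

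- Section 4.1: at consent each patient is "assigned to Group A or Group B using a computer algorithm". Who may know the code is not said.
- Section 4.2: for later sessions, "the position of the hotspot on both hemispheres will be noted on the fabric cap".
- Section 4.5.1: "The research team will place the TMS coil over the hotspot that was located during the familiarisation session", and "On this location (separately for healthy and stroke affected hemisphere), we will measure the patients RMT".
- Section 4.5.2: feedback pulses are given at 120% of RMT. A bar appears on a monitor after each pulse, and for a successful trial "The vertical bar will be green, with a green tick on screen beside it, and a positive sound-byte will be played". Resting MEPs from 20 pulses are recorded once the feedback blocks are over.
- Section 4.5.4: control patients see a bar whose height does not change, with rewards in a predictable pattern. The section asserts that TMS is applied in the same way in both groups.
- Section 4.6: RMT is recorded again at each follow-up as a marker of excitability, and further feedback blocks are given.

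**The concern.** The reason given in section 4.3 makes sense only if the person performing TMS is expected to know the arm. The functional tests are therefore protected, while the outcome named in the hypothesis is not. MEPs are recorded by EMG, but what is recorded depends on where the coil sits and how strong the pulse is, and the team sets both.

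If those choices differ even slightly between arms, the difference looks the same as the hypothesised treatment effect. The assertion in section 4.5.4 that TMS is applied identically would then rest on the operator's good intentions and not on the design. With 10 patients per arm there is little to dilute a few affected sessions, and no later analysis can separate operator influence from a true effect.

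**Working it through.** The protocol states no figure on this point, so there is none to reproduce. The check sets the sections side by side.

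**Step 1: can the arms be told apart on screen?** In the neurofeedback arm the bar follows each MEP and turns green or red against a baseline line (4.5.2). In the control arm its height is fixed (4.5.4). A few trials are enough to recognise which is running.

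**Step 2: is the display kept from the operator?** The patient sits in front of the monitor while pulses are given. No visible sentence screens the monitor, confines the sound to the patient, gives RMT or resting MEPs to a masked person, or masks the A/B code.

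**Step 3: which measurements come after the display could have been seen?**

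| Measurement | Timing relative to feedback | Exposed |
|---|---|---|
| RMT, session 1 | before any feedback | not through the display |
| Resting MEPs, session 1 | after that session's feedback blocks | yes |
| RMT and coil placement, sessions 2 to 4 | after session 1 feedback | yes |
| Resting MEPs, sessions 2 to 4 | after feedback | yes |
| RMT and feedback blocks at 2, 6, 12 and 26 weeks | after all training | yes |

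RMT is measured at 4 training and 4 follow-up sessions, 4 + 4 = 8. Only the first precedes all feedback, so 8 − 1 = 7 of 8 are exposed. Resting MEPs at the end of the training sessions are exposed in 4 of 4.

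**Step 4: does operator judgement reach the outcome?** It can do so by two routes.

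- Coil placement from a cap mark affects feedback and resting MEPs alike.
- RMT fixes the intensity of the feedback trials: intensity = 1.2 × RMT, so an RMT that is off by 1 point of stimulator output moves the intensity by 1.2 × 1 = 1.2 points. Section 4.5.2 does not state the intensity of the resting block, so this second route is documented for the feedback trials only.

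**Step 5: can the effect be sized?** Turning an intensity shift into an MEP change needs each patient's RMT and recruitment curve, and then the difference in RMT error between the arms. The documents give none of these.

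**The case against.** The strongest reply is that MEPs are instrument readings, that the rater-dependent tests do have a separate assessor, and that RMT follows an amplitude rule (more than 50 uV in 5 of 10 trials, section 4.2) and is described before the feedback blocks of each session. Session 1 RMT therefore cannot have been influenced by the display. All of this stands. It narrows the exposure but does not remove it, because coil placement is still a judgement and the RMTs of later sessions follow earlier feedback.

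The RMT route is also partly self-limiting. Setting RMT too high would enlarge MEPs but would record lower excitability on a measure that section 4.6 follows. If the baseline amplitude is taken in the same session at the same intensity, which the protocol does not say, much of the shift would cancel.

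Four stronger readings are tempting and are not supported.

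- *That the operator does see and hear the feedback.* No sentence says so, and the operator's position is not described. The text shows only that nothing prevents it. Sound is the weaker cue: section 4.5.4 says that only what patients see is altered, although a predictable reward pattern might change the sounds too.
- *That one person sets RMT and handles the coil throughout.* Section 4.5.1 speaks of the team. Only section 4.3 refers to a single member who performs TMS.
- *That the bias has a known size.* An assumed recruitment curve would give percentages, but they would describe the effect of an RMT error, not a difference in error between arms.
- *That the resting block is the primary outcome.* Section 1 names MEP amplitude without choosing between resting and feedback-block MEPs.

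Finally, the visible numbering goes from 4.5.2 to 4.5.4. Whether text is missing there cannot be told, so the statement about absent safeguards applies to the visible text.

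**Conclusion.** The point holds as a gap in the design. Carried out as written, the plan allows whoever places the coil and measures RMT to know the arm from the first feedback block on, and the one blinding step it contains implies that this is expected. The exposure covers the later MEPs of session 1, coil placement and RMT from session 2, and every follow-up measurement, that is 7 of the 8 session RMTs. The direction and size of any bias are unknown and cannot be derived from the documents.

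The conclusion assumes that the same operator, or the same small team, serves a patient across sessions, and that no safeguard stands in text that is not visible. It does not show that bias will occur. Who is masked while an outcome is measured is a matter of trial conduct, so it belongs in the protocol and is not something to leave to an analysis plan. It should be settled before patients are trained.

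**What to change.** Add to section 4.5.1, and apply in section 4.6, wording such as:

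> The feedback monitor faces the patient and is out of the sight of the person operating the coil. Sounds reach the patient through earphones. The program loads the feedback type from the patient code without displaying the arm. The operator sees only raw EMG and coil-position information. Patients are asked not to comment on the feedback. For RMT, software counts the responses above 50 uV out of 10.

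RMT is already described before the feedback blocks, so only the counting by software is new there. Earphones are worthwhile even though sound is the weaker cue: an operator who watches the EMG could notice sounds that do not follow the MEPs.

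The cost is a turned or screened monitor, a pair of earphones and a small change to the program, with no extra staff or visits. The drawback is that the operator can no longer coach the patient from the display. Masking may still be imperfect, because patients may comment despite the request.

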4.5.2 TMS neurofeedback block

The patient will be positioned in front of a computer monitor and will receive a block of 20 neurofeedback trials. Each trial contains just one TMS pulse, so in total they will receive 20 TMS pulses (at an intensity that is 120% of the RMT) with an interval of 6-8 seconds between pulses. Each TMS pulse will be followed immediately by feedback on screen in the form of a vertical bar. The height of the bar indicates the amplitude of the MEP recorded in the muscle, and this is shown relative to a horizontal white line that indicates their baseline MEP amplitude. If the current MEP on a given trial is larger than baseline, the trial is deemed 'successful'. The vertical bar will be green, with a green tick on screen beside it, and a positive sound-byte will be played. If the MEP amplitude is below baseline, the trial is unsuccessful; The bar will be red, with a red cross, and a negative sound-byte will be played. Patients will be told that their goal is to accrue as many successful trials as possible, and that the height of the bar can be influenced by imagining movements using the stroke affected limb (specifically, the stroke affected finger muscles).

This block of neurofeedback takes approximately 6 minutes, and is repeated three times during the course of the training session, with rest breaks for the patient between blocks.

At the end of the training session, we will record MEPs from 20 TMS pulses while the patient is at rest, viewing a fixation cross (for pre-post measurement of resting corticospinal excitability).

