4.5.4 Pseudofeedback group

The control (pseudofeedback) group (n=10) will undergo identical procedures to the experimental group, but with the on-screen feedback bar height in the game changed such that it does not represent MEP amplitude, but instead shows a bar of fixed height, with a predictable reward schedule. This prevents learning how to control the bar in the game, and thus allows us to investigate whether patients using the feedback to learn to up-regulate excitability demonstrate better functional upper limb outcomes compared to those who did not. The application of TMS is identical for both groups- the only thing altered is their visual feedback.

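### Section 4.5.2 rewards any MEP above baseline without requiring a quiet muscle before the pulse, so feedback-block MEPs in the neurofeedback arm could partly reflect slight contraction

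*Protocol*

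**What the plan says.** Protocol section 4.5.2 gives the whole reward rule. The bar is tied to the response: "The height of the bar indicates the amplitude of the MEP recorded in the muscle". A trial succeeds "If the current MEP on a given trial is larger than baseline", and success brings a green bar, a tick and a positive sound. The incentive is explicit: "Patients will be told that their goal is to accrue as many successful trials as possible". Patients are also told that "the height of the bar can be influenced by imagining movements using the stroke affected limb", specifically the affected finger muscles.

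Section 2 admits patients with "Low/No residual movement in lower arm and hand" who have MEPs in response to TMS.

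Section 4.5.4 says that the control display "shows a bar of fixed height, with a predictable reward schedule". It does not represent MEP amplitude, and everything else is the same in both arms.

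Each training session ends with 20 pulses at rest in front of a fixation cross (4.5.2). The resting motor threshold (RMT) is recorded at each follow-up (4.6).

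The hypothesis in section 1 is an increase in MEP amplitude compared with the pseudofeedback group. It does not say whether this is tested on MEPs from feedback blocks or from resting blocks.

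**The concern.** Amplitude is the only condition for reward. If a patient slightly tenses the target finger muscle before the pulse and the MEP grows as a result, the rule scores a success, although imagery has changed nothing. The instruction to imagine moving that same muscle makes some tensing plausible. The protocol also expects motor recovery in the first 12 weeks, while feedback blocks continue at 2, 6, 12 and 26 weeks, so the ability to tense may grow during the study.

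The control arm does not cancel this. Controls may tense too, but their display does not reward it. Any reinforcement of contraction therefore works in one arm only, in the direction of the hypothesis.

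Three things are at stake: the meaning of a between-arm difference in feedback-block MEPs, the content of the training itself, and the planned correlation of MEP change with functional improvement. Patients who regain movement could both tense more and score better.

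**Working it through.** The protocol gives no figure on this point, so there is none to reproduce. The check has a textual part and an illustration.

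**Text.** Reading the whole protocol for a condition on muscle activity:

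- 4.2 and 4.5.1 (hotspot, RMT, preparation): arms are supported on pillows and electrodes are placed. No background-EMG limit.
- 4.5.2 (feedback block): reward depends on amplitude against baseline. No pre-pulse check, no withholding of pulse or feedback, no trial rejection, and no instruction to stay relaxed.
- 4.5.2 (end of session): the patient is at rest. No EMG criterion for rest.
- 4.5.4 (control): reward is unrelated to the MEP, and the same gap applies.

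EMG is already recorded (section 1 and 4.5.1), but is described only as the means of measuring the MEP.

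**Illustration 1: mean MEP and success rate with no change in excitability.** All inputs are assumptions, including that contraction enlarges the MEP. MEP amplitude is lognormal with its mean at baseline and per-trial CV of 0.4 or 0.7. A share f of trials carries a contraction that multiplies the MEP by k.

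- s² = ln(1 + CV²)
- Rise in mean MEP = f(k − 1)
- Success rate = (1 − f)·Φ(−s/2) + f·Φ((ln k − s²/2)/s)

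For k = 2 and f = 0.25:

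- Rise in mean = 0.25 × 1 = 25%.
- CV 0.4: s = 0.385; success = 0.75 × 0.424 + 0.25 × 0.946 = 0.554, up from 0.424.
- CV 0.7: s = 0.631; success = 0.75 × 0.376 + 0.25 × 0.783 = 0.478, up from 0.376.

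Over k = 1.5 to 3 and f = 10% to 50%, the mean rises by 5% to 100%. Success rises from 42% to between 46% and 71% (CV 0.4), or from 38% to between 40% and 65% (CV 0.7).

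**Illustration 2: dependence on the control arm.** Let f_N and f_C be the shares of trials with contraction in the neurofeedback and control arms. The spurious log difference is ln[(1 + f_N(k − 1)) / (1 + f_C(k − 1))]. Dividing it by SD × √(2/10) gives the noncentrality of a two-sample t-test with 10 per arm (18 degrees of freedom). With k = 2, an assumed between-patient log-SD of 0.5 or 0.3, and a two-sided 5% test, the chance of a false result favouring neurofeedback is:

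| f_N | f_C | MEP ratio | SD 0.5 | SD 0.3 |
|---|---|---|---|---|
| 25% | 0 | 1.25 | 16% | 35% |
| 25% | 12.5% | 1.25/1.125 = 1.11 | 6.5% | 11% |
| 25% | 20% | 1.25/1.20 = 1.04 | 4% | 5% |
| 25% | 25% | 1.00 | 2.5% | 2.5% |
| 5% | 0 | 1.05 | 4% | 5% |

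With f_N = 25% and f_C = 0, letting k run from 1.5 to 3 widens the range to 7% to 82%. The result is driven by how often each arm contracts, and the documents say nothing about that.

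**The case against.** The strongest reply is that this is an unwritten acquisition detail, not an error. Section 4.5.2 describes what the screen shows and does not say that trials with an active muscle are accepted. Section 1 points to a published implementation of the interface, which may screen background EMG. The section numbers also jump from 4.5.2 to 4.5.4, so something may be missing. Patients have little or no movement, their arms are supported, and they are told to use imagery. The least exposed measures, resting MEPs and RMT, are already collected.

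Much of this stands as a limit on the consequence. Section 1 does not tie the hypothesis to feedback-block MEPs, the resting block involves no described reward, and the entry criterion restricts how many patients could tense at all.

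It does not remove the point. The reward rule is the intervention, and this protocol fixes it. Followed as written, it rewards a contraction-enlarged MEP. A statistical analysis plan could drop such trials afterwards but could not withdraw the reward. Low residual movement still leaves room for slight contraction. The missing section number may be only a slip, and current practice may include EMG monitoring, but nothing in the protocol requires it.

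A reader might go further and infer that the main comparison is shown to be biased, or that the false-positive risk is as high as 82%. The documents support neither. That upper figure needs a threefold effect, the smaller SD, contraction on a quarter of trials in every neurofeedback patient, and none in controls who do the same imagery.

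**Conclusion.** The point holds in limited form. The reward rule in 4.5.2 can reinforce slight contraction, and only in the neurofeedback arm. A between-arm difference in MEPs from feedback blocks could therefore partly reflect contraction and could not be read with confidence as learned up-regulation. Resting MEPs and RMT are less exposed, but are not protected by any stated EMG criterion.

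The direction rests on two assumptions: that slight contraction before the pulse enlarges the MEP, and that some eligible patients can produce it. The size cannot be derived from the documents, and no false-positive figure should be attached to the trial. The illustrations show only that the effect could range from negligible to important, depending on the difference in contraction between arms. The text shows that the gain can arise this way, not that it will. The change is worth making because it is cheap and the training cannot be corrected afterwards.

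**What to change.** Add to 4.5.2, with a cross-reference in 4.5.4:

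- Compute EMG amplitude of the target muscle in a stated window before each pulse, from the EMG already recorded.
- Give a pulse or feedback only if that amplitude is within a prespecified limit set from the patient's own resting recording. The sponsor must choose the window and limit, as the documents supply neither.
- Otherwise delay or repeat the trial with a neutral prompt to relax and no reward. Checking before the pulse is released means a delayed trial adds no pulse.
- Apply the same gate in both arms, to the recording that sets the baseline line, and to the end-of-session resting block.
- Complete each block to 20 valid trials, and run the control reward schedule over valid trials only, so that its predictability is unchanged.
- Report pre-pulse EMG and the number of gated trials by arm, since gating may itself differ between arms.

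The cost is a small software change, a short protocol addition and slightly longer sessions, more so for patients who find it hard to relax the muscle.
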